14.3. SAFETY MONITORING

The medical monitor(s) will review results throughout the study to ensure the continued safety of the investigational device and to ensure that no subjects are exposed to unreasonable risk. The

medical monitor(s) will be notified of SAE and UADE reports through emails as well as other significant safety findings through periodic reports. The medical monitors will be available to answer all questions from investigators. The medical monitors, as well as any other qualified personnel designated by AcuFocus, may also review all reports on the progress of the study (at enrollment and at key postoperative visits). Care will be taken to ensure analyses/reports are not disseminated to investigators/site personnel.

15.0 PUBLICATIONS

AcuFocus, the Sponsor of this evaluation, has a proprietary interest in this evaluation. AcuFocus will have the final decision regarding the publication of any manuscript until the IOL is marketed. Under no circumstances shall the investigator(s) or center personnel publish or disclose AcuFocus' confidential information concerning the evaluation, including the clinical data, without prior written approval from AcuFocus. Authorship will be determined by AcuFocus, based on contribution to the study and enrollment, and established prior to submission of a manuscript.

16.0 RECORD RETENTION

All study-related correspondence, subject records, consent forms, authorization for use/disclosure of health information form, records of the distribution and use of all investigational products, and original source documents should be maintained on file by the investigative site.

The investigator must maintain and have access to the following essential documents for a minimum of five years (or according to local laws and regulations) after completion of the study or until the sponsor informs the site as to when these documents no longer need to be retained:

- All source documents
- All adverse event information (adverse event forms, follow-up letters, etc.)
- Study product supply records/inventory
- IRB and regulatory approval documentation
- Study Correspondence (paper or electronic)
- Site visit documentation
- Protocols and the reason for any deviations from the protocol
- Subject logs
- Completed patient informed consent forms
- Subject medical chart/clinic notes

AcuFocus requires notification in writing if the investigator wishes to relinquish ownership of the data so that mutually agreed-upon arrangements can be made for transfer of ownership to a suitably qualified, responsible person.

17.0 TERMINATION OF THE INVESTIGATION

The clinical investigation will be suspended in the event of unexpectedly high levels of complications and/or the occurrence of adverse events that are unexpected in nature and/or severity. An evaluation of causality will be made to determine the relationship to the investigational IOL. If causality is not shown to be related to the investigational IOL, the study may be resumed in accordance with the IRB and regulations of the governing authorities. The study will be terminated if causality is shown to be related to the investigational IOL.

The clinical investigation will be suspended by AcuFocus if any of the following conditions occur:

- In the event of severe and alarming adverse events that have not been previously anticipated in nature and/or severity
- Government agencies or IRB, upon review of clinical investigation data and/or adverse event reports, find the level of complications and/or adverse events unacceptable for continuation of the investigation
- Unacceptable clinical performance of the investigational IOL (i.e., decreased visual acuity results, unacceptable incidence, bother or intensity of subjective visual symptoms, etc.) as deemed by AcuFocus and/or the Medical Monitors

AcuFocus may stop the study at any time for reasons it determines appropriate. However, no suspension of the study will be made to disadvantage the subjects participating in the study. Following suspension of the study for any reason, all subjects who have already received an investigational IOL will continue to be followed through completion of the 12-month postoperative course.

18.0 DATA ANALYSIS METHODS

This section (section 18.0 through 18.4) highlights the key statistical methods and analyses planned for this study. The SAP includes details for all statistical methods, plans, adverse events reporting methods, and sample size calculations for the study.

Some key data and analysis conventions include the following:

For the primary and secondary effectiveness endpoints, the six-month postoperative visit will be the primary analysis time point unless otherwise noted. For the primary safety endpoints, the 12-month study visit will be the primary analysis time point.

Binocular safety and effectiveness analyses will compare the test group and the control group. Monocular safety and effectiveness analyses will compare the IC-8 IOL eyes and the monofocal fellow eyes within the test group. All co-primary effectiveness and safety endpoints have to be met to claim overall effectiveness and safety success. There is one secondary effectiveness endpoint regarding the tolerance to astigmatism in IC-8 IOL eyes, and this endpoint will only be tested when all co-primary effectiveness endpoints have been achieved. Under this plan, type I error rates will be controlled at a significance level of 0.05 per individual hypothesis without adjustment for multiplicity under any family. Other statistical comparisons in the additional analyses and supportive analyses should not be used for the purpose of claims.

18.1. ANALYSIS POPULATION

For the primary effectiveness endpoints, the primary analysis population will be an ITT (Intentto-Treat) analysis. The ITT population includes all subjects who are fully enrolled and are binocularly implanted in the study. For the secondary effectiveness endpoint, the primary analysis population will be a mITT (modified Intent-to-Treat) analysis for all eyes implanted with IC-8 IOL and achieving BCDVA 20/25 or better. For eyes that do not have data available at the 3-, 6- or 12-month visits, data will be imputed according to the imputation methods specified in the SAP.

A Per-Protocol (PP) analysis will also be performed on the primary and secondary effectiveness endpoints to support the primary ITT analysis. The PP population will include eyes from binocularly implanted subjects, evaluated within the proper study interval and without major protocol deviations as determined prior to database lock, and evaluated at least two weeks after any SSIs. Major protocol deviations to be excluded from PP analysis are: those related to inclusion, exclusion or qualification criteria, and/or those that have the potential to either positively or negatively affect the primary and secondary study endpoints, including uncorrected or distance-corrected visual acuities, refraction, contrast sensitivity, and are unrelated to the study procedure or the study device; and they will be specified prior to database lock.

PP analyses will only include available data at the time of analysis (i.e., no data imputation). For the primary effectiveness endpoints, the PP population is usually a subset of the ITT population; for the secondary effectiveness endpoint, the PP population is usually a subset of the mITT population.

For all key safety endpoints, the primary analysis population will be the safety analysis population. The safety population will consist of all subjects who complete enrollment and have been bilaterally implanted and those subjects not successfully implanted with the IC-8 IOL but for whom the IC-8 IOL touched the eye. Safety analyses will only include available data at the time of analysis (i.e., no data imputation). Reporting of cumulative complications (occurring at any time postoperative) will include data from all subjects in the safety population. Test subjects who have undergone the IC-8 IOL surgery with attempted but failed implantation will be followed until all ocular adverse events are resolved or stable before being exited from the study, and they will be counted in the safety population.

The safety population (with no imputation) will also be used for reporting of other postoperatively measured clinical parameters that are not discussed as part of the key effectiveness or safety endpoints.

The primary reporting will be on IC-8 IOL eyes and fellow eyes in the test group or binocular outcomes from both test and control groups. However, key data such as visual acuity, refractive error, medical/lens complications and adverse events will also be reported separately for first and second eyes in the control group.

Besides the ITT (or mITT) and PP populations, key effectiveness outcomes and key safety outcome of BCDVA may also be reported for best-case subjects where appropriate. A best-case subject is defined in ISO 11979-1:2012 as a subject with no preoperative ocular pathology, no macular degeneration detected at any time, and no previous surgery for the correction of refractive errors. In this study, a best-case subject should also have no significant macular pathology at any time. Both eyes must meet the best-case criteria for inclusion in the best-case analysis.

Subjects who are disqualified prior to second-eye implantation will not be counted toward the study cohort or any analysis population. For the disqualified subjects, a listing of UCDVA and BCDVA at preoperative and before study exit will be tabulated, as well as any adverse events; no other analysis will be performed.

In addition to the above analysis populations, additional best-case analyses and exploratory subgroup analyses may also be performed as specified in the SAP.

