7.2. EXCLUSION CRITERIA (all criteria apply to each eye)

- 1. Requiring an IC-8 intraocular lens outside the available spherical power range of +15.5 D to +27.5 D;
- 2. Pharmacologically dilated pupil size less than 6 mm in either eye;
- 3. Inability to achieve stable keratometric readings for contact lens wearers (difference in corneal astigmatism between two visits at least 1 week apart following discontinuation of contact lens wear is within ± 0.50 diopter in magnitude and within $\pm 15^{\circ}$ in axis);
- 4. Patients with irregular astigmatism in either eye;
- 5. Preoperative corneal astigmatism > 1.50 diopters in either eye (as assessed by biometry keratometric readings);
- 6. Active or recurrent anterior segment pathology (chronic uveitis, iritis, iridocyclitis, rubeosis iridis, Reiter's syndrome, etc.);
- 7. Presence of ocular abnormalities other than cataract such as:
 - a. Corneal abnormalities other than regular corneal astigmatism up to 1.50 diopters
 - b. Pupil abnormalities
 - c. Strabismus or amblyopia
 - d. Capsular or zonular abnormalities
 - e. Glaucomatous retinal nerve fiber changes
 - f. Recurrent and/or persistent intraocular inflammation

- g. Known pathology that may affect visual acuity and/or is predicted to cause future acuity losses to a level of worse than 20/25 BCDVA (e.g., macular degeneration)
- 8. Diagnosis of dry eye in which patients are unable to maintain eye comfort or adequate vision even with dry eye medication;
- 9. Congenital bilateral cataracts;
- 10. Previous corneal or intraocular surgery, except pterygium surgery, which may be allowed, based meeting all other inclusion/exclusion criteria;
- 11. History of ocular trauma or ocular conditions expected to require retinal laser treatment or other surgical intervention;
- 12. Use of systemic or ocular medications that may affect vision or likely to impact pupil dilation or iris structure, such as any prior or current use of tamsulosin or silodosin (alpha-adrenergic antagonist medications, e.g., Flomax, Flomaxtra, Rapaflo), which are likely to cause poor dilation or lack of adequate iris structure to perform standard cataract surgery;
- 13. Acute, chronic or uncontrolled systemic disease that would, in the opinion of the investigator, increase the operative risk or confound the outcomes of the study (e.g., immune compromised, connective tissue disease, hypertension, Type I & II diabetes etc.);

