
Blue-blocking IOLs are not allowed in this trial.

Slit-Lamp Biomicroscopy:

A biomicroscopic slit-lamp exam will be performed preoperatively to rule-out any anterior segment abnormalities other than cataract. The type and density of cataract should be graded using the grading shown in **Appendix C**.

Ocular Surface Assessments:

Ocular surfaces will be assessed by tear break-up time (TBUT) and corneal staining using the Oxford Grading Scale.

Dilated Fundus Evaluation with Binocular Indirect Ophthalmoscopy (BIO), and Slit-Lamp Fundus Exam (SLE):

Dilated fundus exam with the BIO, and slit-lamp examination with a +90 D lens will be performed preoperatively on all eyes in both groups, in keeping with the standard of care of

patients undergoing cataract surgery with intraocular lens implantation. The investigator will be required to rate the level of difficulty with retinal evaluation and their ability to achieve a stereoscopic view of the posterior pole in both eyes of the test subjects, preoperatively **(Appendix D)**. Investigator responses will be recorded on the source documents. If the site routinely performs dilated slit-lamp fundus exam with a lens other than a +90 D lens, the site will be allowed to use their preferred lens to perform standard of care to view the retina. The lens of choice, if other than a +90 D lens, will be collected on the source documents.

NOTE: Grading of the level of difficulty with retinal evaluation must be performed by the principal investigator or the operating surgeon.

Spectral Domain Optical Coherence Tomography (SD-OCT):

Preoperatively, dilated SD-OCT exam must be performed to rule out retinal and macular pathologies (e.g., epi-retinal membrane, age-related macular degeneration) in all eyes from the control and test groups. Assessment of normal vs. abnormal findings from dilated SD-OCT exam will be captured in the source documents.

Retinal Diagnostic Testing (subgroup):

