The Investigator may choose to measure toric IOL axis at any postoperative visit, if deemed necessary by the investigator. The assessment has to be performed with a slit lamp after the pupils are pharmacologically dilated. The slit lamp reticule should be used to measure the IOL axis.

Ocular Surface Assessments:

Ocular surfaces will be assessed by tear break-up time (TBUT) at 3, 6, and 12 months and by corneal staining at 3, 6, and 12 months for both eyes and additionally at 1 week and 1 month for the first eye (to complete at 1 month only if the first eye has not passed the SPK qualification criteria at 1 week).

Intraocular Pressure:

Intraocular pressure is to be measured using Goldmann applanation at Day 1, Week 1 and 1, 3, 6 and 12 months postoperatively. It is required that the same method be used for all patients at the site for the duration of the study.

Dilated Fundus Evaluation with Binocular Indirect Ophthalmoscopy (BIO), and Slit-Lamp Fundus Exam (SLE):

Dilated fundus exam with the BIO and slit-lamp examination with a +90 D lens will be performed postoperatively at 12 months on all eyes in both groups, in keeping with the standard of care of patients undergoing cataract surgery with IOL implantation. The surgeon will be required to rate the level of difficulty with retinal evaluation and achieving a stereoscopic view of the posterior pole in both eyes, postoperatively (**Appendix D**). Surgeon responses will be recorded on the source documents. If the site routinely performs dilated slit-lamp fundus exam with a lens other than a +90 D lens, the site will be allowed to use their preferred lens to perform standard of care to view the retina. The lens of choice if other than a +90 D lens will be collected on the source documents.

NOTE: Grading of the level of difficulty with retinal evaluation must be performed by the principal investigator or the operating surgeon.

Retinal Diagnostic Testing (subgroup):

The following assessments will be performed at the 3-month postoperative visit in the subgroup.

- 1. Undilated Visual Field (SITA Standard 30-2)
- 2. Dilated Spectral-Domain Ocular Coherence Tomography (SD-OCT) images
- 3. Dilated fundus photography

The results and images from all retinal testing should be saved and submitted to the reading center. The same instruments must be used both preoperatively and postoperatively. The testing protocols listed in **Table 5** should be repeated at the 3-month postoperative visit.

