c. The proportion of best-case IC-8 eyes achieving BCDVA 0.3 logMAR or better is not less than the safety and performance endpoints (SPE) rate listed in ISO 11979-7:2014 Table B.4. The comparison between the proportion for the best-case IC-8 eyes and the SPE rate for posterior chamber IOL (96.7%) will be performed using the exact test based on binomial distribution at $\alpha = 0.05$ (one-sided). The null hypothesis is that the proportion for the best-case IC-8 eyes is not less than 96.7%. The alternative hypothesis is that the proportion for the best-case IC-8 eyes is less than 96.7%. Formally put as follows:

$$\begin{split} &H_0 {:} \ p_T \geq 96.7\% \\ &H_A {:} \ p_T < 96.7\% \end{split}$$

Where p_T is the proportion of best-case IC-8 eyes achieving BCDVA 0.3 logMAR or better and 96.7% is the SPE rate for posterior chamber IOL.

As specified in ISO 11979-7:2014, the statistical success criterion is when H_0 is not rejected, i.e. the test result is a p-value greater than 0.05, demonstrating the proportion of best-case IC-8 eyes achieving BCDVA 0.3 logMAR or better is not less than the SPE rate.

Note that a best-case subject is defined in Section 18.1 Analysis Population of this study protocol. For this analysis, only the IC-8 eye but not both eyes of a subject has to meet the best-case criteria.

- 2. Rates of ocular adverse events (the rate of adverse events are based on the proportion of eyes with events cumulative or persistent through database lock, as applicable):
 - a. For each type of adverse event listed in the ISO 11979-7:2014 Table B.2, the rate for the IC-8 IOL eyes is not statistically greater than the SPE rate for that event. The comparison between the adverse event rate for the IC-8 eyes and the SPE rate for posterior chamber IOL for each adverse event will be performed using the exact test based on binomial distribution at $\alpha = 0.05$ (one-sided). The null hypothesis is that the adverse event rate for the IC-8 eyes is not greater than SPE rate. The alternative hypothesis is that the adverse event rate for the IC-8 eyes is greater than the SPE rate. Formally put as follows:

$$\begin{split} H_0: p_T &\leq \hat{p} \\ H_A: p_T > \hat{p} \end{split}$$

Where p_T is the adverse event rate for the IC-8 eyes and \hat{p} is the SPE rate, for each adverse event listed in ISO 11979-7:2014 Table B.2.

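### Co-primary safety test 1c uses a best-case set narrower than the ISO definition it quotes: an added macular clause acts mainly on pathology found after surgery, yet the ISO rate of 96.7% is kept.

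*Combined protocol and SAP*

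**What the plan says.** Section 18.1 takes its best-case definition from ISO 11979-1:2012: "no preoperative ocular pathology, no macular degeneration detected at any time, and no previous surgery for the correction of refractive errors". The next sentence adds a criterion for this trial: "In this study, a best-case subject should also have no significant macular pathology at any time".

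Item 1c of Section 18.3.1 tests the proportion of best-case IC-8 eyes with 12-month BCDVA of 0.3 logMAR or better against 96.7%, the rate in ISO 11979-7:2014 Table B.4. The test is exact binomial at one-sided 0.05 and succeeds when the null is not rejected. On the population, item 1c says: "Note that a best-case subject is defined in Section 18.1 Analysis Population of this study protocol". It makes one change: "For this analysis, only the IC-8 eye but not both eyes of a subject has to meet the best-case criteria". The added macular clause therefore stays in force for the IC-8 eye.

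Item 1b applies the same acuity threshold to all IC-8 eyes, against 92.5%. Section 18.3 requires every co-primary safety endpoint to be met.

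Four other places bear on how the clause works:
- Section 7.2, item 7g, excludes before enrolment: "Known pathology that may affect visual acuity and/or is predicted to cause future acuity losses".
- Section 9.3 requires imaging of every eye: "Preoperatively, dilated SD-OCT exam must be performed to rule out retinal and macular pathologies".
- Section 9.7 schedules a dilated fundus examination that "will be performed postoperatively at 12 months on all eyes in both groups". Appendix A assigns it to a non-masked examiner.
- Section 10.2.1 lists cystoid macular edema among potential adverse events and defines it partly by a drop in BCDVA to 20/40 or below.

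**The concern.** A one-sample test against a historical rate is interpretable when the eyes tested are selected in the same way as the eyes behind the rate. Here the plan quotes the definition, narrows it and keeps the rate. Nothing in the supplied text says that 96.7% applies to the narrower set.

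The narrowing also depends on what is found after the lens is in. A macular finding after surgery can be tied to the acuity under test, and cystoid macular edema is tied to it by definition. An eye that would count as a failure in 1c can thus leave the denominator because of the condition that made it fail. The supplied text does not say what makes macular pathology *significant*, who decides, or when.

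At stake is the stricter of the two acuity-rate tests in the co-primary safety set.

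**Working it through.** **Step 1. What the added clause can act on.**

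| Macular finding in the IC-8 eye | Removed by the quoted ISO definition? | Removed only by the added clause? |
|---|---|---|
| Any pathology known before surgery | Yes (and screened by 7g and SD-OCT) | No |
| Macular degeneration, found at any time | Yes | No |
| Other macular pathology first found after surgery | No | Yes, if judged significant |

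Only the third row is left. It mixes disease the cataract hid with disease that arose after surgery.

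**Step 2. Inputs.** From Section 18.3.1: reference rates 96.7% (1c) and 92.5% (1b), one-sided alpha 0.05, pass if p > 0.05. The supplied text gives no best-case sample size, failure allowance or power for 1c, so there is no plan figure to reproduce. Assumed: n = 300, the test-arm completion target. Failure rates and exclusion rates are also assumptions, shown as ranges.

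**Step 3. Allowance in 1c.** With f failures in n eyes, p = P(X ≥ f), X ~ Binomial(n, 0.033).
- 285/300 (15 failures): p = 0.075, pass.
- 284/300 (16 failures): p = 0.043, fail.

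Removing failing eyes so that 15 failures remain:

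| Full set | Result | Failing eyes removed | Reduced set | Result |
|---|---|---|---|---|
| 16/300 fail acuity | fails 1c | 1 | 284/299 | p = 0.073, pass |
| 17/300 | fails 1c | 2 | 283/298 | p = 0.072, pass |
| 18/300 | fails 1c | 3 | 282/297 | p = 0.070, pass |
| 19/300 | fails 1c | 4 | 281/296 | p = 0.069, pass |

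**Step 4. Whether 1b catches it.** With X ~ Binomial(300, 0.075), 30 failures give p = 0.067 (pass) and 31 give p = 0.045 (fail). At 284/300, 1b gives p = 0.94. If all 300 eyes are best-case, results of 16 to 30 failures pass 1b and fail 1c.

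**Step 5. Probability of passing 1c.** Let q be the true failure rate, r the share of eyes excluded by the clause, and s the share of those that would have failed. The number excluded is K ~ Binomial(300, r). The failure rate among the rest is (q − rs)/(1 − r), and the allowance is recomputed at 300 − K. Example: q = 5%, r = 1%, s = 1 gives (0.05 − 0.01)/0.99 = 4.04%.

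Pass probability (%) for r = 0 / 0.25% / 0.5% / 1%:

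| q | all excluded eyes would fail | half would fail |
|---|---|---|
| 2% | about 100 throughout | about 100 throughout |
| 3.3% | 95.7 / 97.7 / 98.9 / 99.8 | 95.7 / 96.8 / 97.7 / 98.9 |
| 4% | 84.9 / 89.8 / 93.5 / 98.0 | 84.9 / 87.5 / 89.8 / 93.5 |
| 5% | 56.8 / 64.6 / 72.1 / 84.9 | 56.8 / 60.7 / 64.6 / 72.1 |
| 6% | 27.9 / 34.3 / 41.4 / 56.8 | 27.9 / 31.0 / 34.3 / 41.4 |

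Other sizes, at q = 5% with all excluded eyes failing: n = 250 gives 62.9 / 69.8 / 76.2 / 86.9; n = 340 gives 56.4 / 64.7 / 72.6 / 85.9.

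**Step 6. The clause does not always help.** If no excluded eye would have failed, pass probability is unchanged at n = 250, 300 or 340. At an allowance boundary it can fall: 291/307 passes (p = 0.0504), but losing one successful eye gives 290/306, which fails (p = 0.0493).

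**The case against.** Several points on the other side are sound, and they limit what can be said.

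- **The SAP.** Sections 18.0 and 18.4 leave detail to a separate SAP, whose text was not supplied. A reader might infer that the exclusion is open to choice after the results are known. The documents do not support that: the SAP may define the term and fix the decision. A definition alone would still leave a set narrower than the quoted ISO one.
- **Found after is not arising after.** Every eye enters with a cataract reducing BCDVA to 20/40 or worse, with or without glare. Disease missed before surgery can appear once the lens is out, and excluding it fits the idea of a best case. This explains the clause but does not separate such eyes from complications.
- **ISO precedent.** The quoted definition itself excludes macular degeneration whenever detected. The complaint is therefore about widening that convention, not about postoperative exclusion as such.
- **Device harm.** A reader might infer that device-caused macular damage is being removed from the safety assessment. Section 10.3 names no macular disease among the device risks; the route the documents show is surgical. Excluded eyes also stay in 1a and 1b, if measured, and in adverse-event reporting.
- **Masking.** A reader might infer an unmasked endpoint. Section 9.7 equates BCDVA with DCDVA, and Appendix A assigns DCDVA to the masked examiner. Only the fundus finding comes from a non-masked one.
- **The per-protocol rule.** Section 18.1 limits certain per-protocol exclusions to deviations that affect endpoints "and are unrelated to the study procedure or the study device; and they will be specified prior to database lock". That rule governs protocol deviations in a supportive effectiveness set, and macular disease is not a deviation. It is an analogy, not a contradiction.

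What stands is the mismatch between set and rate, and the possibility that a postoperative complication removes a failing eye from 1c.

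**Conclusion.** The point holds in a limited form. Test 1c compares a set narrower than the quoted ISO best-case definition with the ISO best-case rate, and the narrowing acts mainly on macular pathology found after surgery.

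The size is conditional. On the assumed 300 eyes, one excluded failing eye is enough to reverse a result at the boundary. Across assumed true failure rates, the effect is nil at 2% and at most about 4 percentage points at 3.3% (95.7% to 99.8%). It becomes material only from about 4%, which is above the 3.3% that the reference rate implies. It requires non-degenerative macular disease that leaves the eye worse than 0.3 logMAR at 12 months; an eye at exactly 0.3 logMAR is a success, and edema may have resolved by then. The documents give no rate for such eyes.

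The effect is confined to 1c. Overall safety success still needs 1a, 1b, the adverse-event tests and the removal limit. This should be changed because the remedy is cheap and the endpoint is co-primary; it is not evidence that the safety conclusion would be wrong.

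**What to change.** - Run the 1c test on the ISO best-case definition exactly as Section 18.1 quotes it, for the IC-8 eye only, without the added clause. Limiting the clause to preoperative pathology is not a useful alternative: the quoted definition already excludes that, so the clause would do nothing.
- Report the narrower set as a supportive analysis. Define *significant macular pathology*, and classify each eye before database lock without knowledge of BCDVA.
- List the eyes that the clause excludes, with their 12-month BCDVA.
- If the SAP already contains any of this, refer to it in Section 18.3.1, item 1c.

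The cost is protocol and SAP wording, one supportive table and a short listing, with no new visits or tests. The downside for the sponsor is that the 1c figure may be slightly less favourable.
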